#### 4.1.4. Safety Endpoints

Safety and tolerability will be assessed based on the incidence and severity of AEs and serious adverse events. Additionally, subjects will be monitored before, during, and after each dose to monitor for changes in vital signs.

#### 4.2. Study Subjects

##### 4.2.1. Definitions of Analysis Sets

Efficacy Analysis Set: The Efficacy Analysis Set is the group of subjects who had both a  $^{129}\text{Xe}$  MRI scan and a  $^{133}\text{Xe}$  scintigraphy scan, and for whom both scans met quality control criteria for analysis. The primary and the 6-zone analysis secondary efficacy endpoints will be analyzed using the Efficacy Analysis Set.

Post-operative Analysis Set: The Post-operative Analysis Set is the group of subjects that met the criteria for inclusion in the efficacy analysis set, and had a post-operative FEV1 (spirometry) value. The post-operative secondary endpoint will be analyzed using the Post-operative Analysis Set.

Safety Analysis Set: The Safety Analysis Set is the group of subjects who received at least 1 dose of either hyperpolarized  $^{129}\text{Xe}$  or  $^{133}\text{Xe}$ . Safety endpoints will be analyzed using the Safety Analysis Set.

Unless otherwise specified, the number and percentage of subjects in each analysis set will be summarized by treatment sequence using descriptive statistics. This and similar summaries will be presented by treatment sequence because the washout period between scans is generally short.

##### 4.2.2. Subject Disposition

Subject disposition will be summarized by treatment sequence for all randomized subjects. The number and percentage of subjects who completed or discontinued prematurely from the study and their reason for discontinuation will be summarized by treatment sequence.

In addition, the number of subjects screened, the number and percentage of screen failures, and their primary reason for screen failure will be summarized.

##### 4.2.3. Protocol Deviations

Protocol deviations will be identified, reviewed and documented by the clinical team prior to database lock. Protocol deviations will be summarized by deviation categories and treatment sequence for all subjects. The listing for protocol deviations, in addition to containing treatment sequence, subject number, visit, and deviations (by categories), will also contain several categories of demographic information.

#### 4.2.4. Demographic and Baseline Characteristics

Demographic and other baseline characteristics for the Efficacy, Post-operative, and Safety Analysis Sets will be summarized for each treatment sequence using descriptive statistics, separately. Continuous demographic and baseline variables include age, height, weight, body mass index, peripheral capillary oxygen saturation (SpO2) at screening, current cigarettes/day, and pack-years of smoking; categorical variables include sex, race, ethnicity, current smoking status, and Hypothetical Assessment of Resection Location.

#### 4.2.5. Medical History

All medical histories as documented by the Medical and Surgical History eCRF will be coded using the Medical Dictionary for Regulatory Activities (MedDRA) Version 20.1.

The number and percentage of subjects with any medical history will be summarized by System Organ Class (SOC) and preferred term (PT) for each treatment sequence based on the Safety Analysis Set.

#### 4.2.6. Vital Signs and Physical Examination at Screening

Results of vital signs and physical examinations at screening will be summarized for each treatment sequence using descriptive statistics.

#### 4.2.7. Prior and Concomitant Therapy

All investigator terms for medications recorded in the eCRF will be coded using the World Health Organization Drug Dictionary Version 01 September 2017.

Prior medications are defined as medications that stopped before the first dose of study product. Concomitant medications are defined as medications that (1) started before the first dose of study product and are continuing at the time of the first dose of study product, or (2) started on or after the date of the first dose of study product.

The number and percentage of subjects who take concomitant medications will be summarized using the Safety Analysis Set by treatment sequence, Anatomical Therapeutic Chemical (ATC) class, and PT. If a subject takes the same medication for the same ATC class or PT, the subject will be counted only once for that ATC class or PT. Prior and concomitant medications will be listed separately.

Oxygen flow rate for subjects who used supplemental oxygen will be summarized using descriptive statistics.

Patients who used an inhaler will be summarized using descriptive statistics.

#### 4.2.8. Exposure to Study Treatments

The polarization (%) of  $^{129}\text{Xe}$  and the dose amount of  $^{133}\text{Xe}$  will be summarized using descriptive statistics. One summary will include data for only those subjects who received only 1 full dose of  $^{129}\text{Xe}$  in addition to their dose of  $^{133}\text{Xe}$ . A second summary will include data for only those subjects who took 2 full doses of  $^{129}\text{Xe}$  in addition to their dose of  $^{133}\text{Xe}$ .

The duration between the time of dosing with  $^{129}\text{Xe}$  and the time of polarization will be summarized using descriptive statistics. As in the paragraph above, there will be separate summaries for subjects with only 1 full dose of  $^{129}\text{Xe}$  and subjects with 2 full doses of  $^{129}\text{Xe}$ .

### 4.3. Data Analysis General Considerations

#### 4.3.1. Handling of Missing Data

Except for the AE causal relationship to the study drug and AE severity (see [Section 4.6.1](#)), missing values will not be substituted by estimated values, but treated as missing in the statistical evaluation. Missing efficacy values are not anticipated as all subjects included in the efficacy analysis set must provide acceptable images for both  $^{129}\text{Xe}$  MRI and  $^{133}\text{Xe}$  scintigraphy. All data from all subjects dosed in the study will be included in all listings, plots, summary tables, and statistical analyses when appropriate.

#### 4.3.2. Visit Windows

There are no visit windows for this study, while time windows are allowable for study assessments as shown in [Appendix 11.1](#). For the statistical analyses, data will be analyzed by their time point of collection.

### 4.4. Efficacy Analyses

Unless specified otherwise, the efficacy endpoints will be summarized and analyzed using the Efficacy Analysis Set.

#### 4.4.1. Primary Efficacy Analysis

The primary analysis for this study will be to test the mean difference in the predicted proportion of remaining function as measured using hyperpolarized  $^{129}\text{Xe}$  MRI relative to the value as measured by  $^{133}\text{Xe}$  scintigraphy (reference standard). The primary analysis will be conducted by estimating the two-sided 95% confidence interval (CI) for the mean difference in predicted proportion of remaining function from the 2 methods.

[figure not shown]
The calculation of the predicted proportion of remaining function will be based on pre-operative imaging and the extent of planned lung resection. The scans will be quantified using commercially available software to report the fraction of activity arising from each of 6 lung

zones, 3 in each lung (refer to [Figure 1](#)). On the eCRF, the surgeon will check the zones that are planned for resection.

The predicted proportion of remaining function will be calculated by subtracting the percentage of function contributed by the zone(s) planned for resection from the total percentage of pre-operative function for all 6 zones. The sum of the resected zone(s) plus the non-resected zones equals 100%. For example, assume that the quantified fractions of activity for zone 1 to zone 6 are 15%, 20%, 25%, 10%, 15% and 15%, respectively and the surgeon notes that zone 4 and zone 5 are planned for complete resection. Then, the predicted proportion of remaining function would be:

$$100\% - (\text{zone 4}[\%] + \text{zone 5}[\%]) \text{ or;}$$
$$(15\%+20\%+25\%+10\%+15\%+15\%) - (10\% + 15\%) = 75\% \text{ remaining}$$

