### 3. JUSTIFICATION OF EQUIVALENCE MARGIN

The acceptable equivalence margin between the predicted proportion of remaining function from  $^{129}\text{Xe}$  MRI and  $^{133}\text{Xe}$  scintigraphy is justified based on literature describing both variability and equivalence margin for the currently available pulmonary function imaging techniques, the ventilation-perfusion scan in the field of lung resection and pneumonectomy (Tulchinsky et al., 2017, Wernly et al., 1980, Win et al., 2006). This literature permits both variability and equivalence margin to be determined by converting the typical predicted post-operative FEV1 values back to their underlying zonal function percentages. From prior literature, the equivalence margin between the 2 imaging techniques currently used for resection planning is 0.3 L (Mariano-Goulart et al., 2006). In this work, the cohort that underwent pneumonectomy, had a mean pre-operative FEV1 of 2.02 L. Assuming the removed lung contributed 50% of total function, the equivalence margin of 0.3 L converts in percentage terms to  $\pm 14.7\%$ . This same work, showed that in the pneumonectomy population the intra-subject variability for  $^{133}\text{Xe}$  scintigraphy leads to an estimated variability in predicted post-operative FEV1 of 0.17 L. Thus, using similar calculations suggests the intra-subject standard deviation for  $^{133}\text{Xe}$  can be estimated in percentage terms to be  $\pm 8.3\%$ . We thus seek to demonstrate an equivalence margin of 14.7% between the imaging tests.

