**Figure 1**      **6 Lung Zones**

The sample mean ( $\bar{d}$ ) and standard deviation (sd) of the within-subject difference of the predicted remaining proportion of function between the two methods will be estimated and the 95% CI for the mean difference will be computed using the standard formula

$$\bar{d} \pm t(n-1, 0.975) * sd / \sqrt{n},$$

where  $t(n-1, 0.975)$  denotes the 97.5th percentile of the t distribution with  $n-1$  degrees of freedom. If the 95% CI for the mean within-subject difference of the predicted remaining proportion of function from each scan is contained within the interval (-14.7%, +14.7%), equivalence will have been demonstrated. In terms of a hypothesis testing framework, let  $\Delta$  denote the true mean within-subject difference. The null ( $H_0$ ) and alternative ( $H_A$ ) hypotheses are:

$H_0: |\Delta| > 14.7\%$

$H_A: |\Delta| < 14.7\%$

The listing for the efficacy data will present data for all 6 zones for both imaging methods and indicate the zones expected to be resected.

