#### 4.4.2. Secondary Efficacy Analyses

##### 4.4.2.1. By-Zone Analysis

The by-zone secondary analysis for this study will be evaluated by comparing the individual percentage function assessments (fraction of ventilation) from each of the 6 zones as derived from the  $^{129}\text{Xe}$  and the  $^{133}\text{Xe}$  ventilation images. The equivalence analysis will be conducted using similar methodology to that in the primary efficacy analysis, and the equivalence margin will be  $\pm 5$  percentage points. Thus, for each of the 6 zones, equivalence will have been demonstrated if the 95% CI for mean difference between the 2 methods is contained within the interval (-5%, +5%).

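### The primary mean pools right- and left-sided planned resections, so a fixed left-right bias of 129Xe MRI largely cancels when the sides are roughly balanced, and the primary rule cannot show it

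*SAP*

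**What the plan says.** Under SAP 4.4.1 each scan is reduced to shares of activity in six "zones, 3 in each lung". The subject's own zones enter the endpoint: "On the eCRF, the surgeon will check the zones that are planned for resection". Predicted remaining function is 100% minus the shares of those zones, and the shares are closed: "The sum of the resected zone(s) plus the non-resected zones equals 100" percent.

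The primary analysis consists of "estimating the two-sided 95% confidence interval (CI) for the mean difference in predicted proportion of remaining function from the 2 methods". If that interval "is contained within the interval (-14.7%, +14.7%), equivalence will have been demonstrated". The hypotheses in SAP 4.4.1 are likewise about a single mean.

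Side of resection does not enter the primary model and is not among the subgroups in SAP Section 6. Resection location is only a summarised baseline variable (SAP 4.2.4). Two further analyses bear on the point:

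- **By zone (SAP 4.4.2.1, secondary).** A separate rule applies zone by zone: "equivalence will have been demonstrated if the 95% CI for mean difference between the 2 methods is contained within the interval", here 5 points either way.
- **Patient level (SAP 4.5.2, exploratory).** The proportion of patients beyond 14.7 points and beyond narrower ranges is reported, with no pass limit.

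**The concern.** The objective is equivalence for evaluating pulmonary function, and Protocol 3.2 says regional function guides surgical decisions. Suppose 129Xe MRI systematically gives the right lung too large a share. Then it understates remaining function for every right-sided candidate and overstates it for every left-sided one. This is one fixed error of the method, not scatter between patients, but the endpoint reverses its sign according to where the lesion lies. A mean over both sides then says more about the side mix of the sample than about whether the scans agree on left-right distribution. The trial could report primary equivalence while the two scans differ by more than the margin in how they divide function between the lungs.

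**Working it through.** **1. The plan's own figures.** SAP Section 2 gives 15 and 32 subjects for 90% power at a margin of 0.3 L, with variability of 0.21 and 0.32 L. An exact paired two one-sided tests calculation (2.5% per side, true difference 0) reproduces both if the stated variability is a per-method SD, so that the SD of the difference is √2 times as large: n = 15 (power 0.906) and n = 32 (power 0.905). Read directly as the SD of the difference, the figures would give 9 and 17. By the same logic, the 8.3 points in SAP Section 3 give a lung-level SD of the difference of √2 × 8.3 = 11.7 points.

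**2. Algebra.** Let δ_z be a subject's 129Xe minus 133Xe difference in zone z. The subject's primary difference is D = −Σδ_z over the planned zones, and closure gives Σδ_z = 0 over all six. Let b_z be the mean bias in zone z, taken as unrelated to planned location, and p_z the fraction of subjects whose plan includes zone z. Then

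E(mean D) = −Σ p_z b_z = −Σ (p_z − p̄) b_z.

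This is zero for any bias if all zones are equally often planned. For a shift of B points from left to right lung, spread evenly over zones, a k-zone resection has expected difference −kB/3 on the right and +kB/3 on the left. The pooled mean is (B/3) × k̄ × (p_L − p_R), where k̄ is the mean number of zones and extent does not depend on side.

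**3. Hand checks** (n = 32, SD 11.7, t = 2.04)

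- Whole lung, B = 15, exactly 16:16: mean 0; SD of D ≈ √(11.7² + 15²) = 19.0; half-width 2.04 × 19.0/√32 = 6.9. The interval is well inside 14.7.
- Mix of 40% one, 40% two and 20% three zones (k̄ = 0.4 + 0.8 + 0.6 = 1.8), B = 15, 60:40 right to left: mean 5 × 1.8 × (0.4 − 0.6) = −1.8.
- Whole lung, B = 16, 75:25: mean 16 × (0.25 − 0.75) = −8.0; SD ≈ √(11.7² + 13.9²) = 18.2, where 13.9 = 2 × 16 × √(0.75 × 0.25); half-width 6.6. The lower limit is about −14.6, so passing is close to a coin toss.
- Right-lung share: half-width 2.04 × 11.7/√32 = 4.2. At B = 15 the interval is about 10.8 to 19.2 (fails); at B = 0 it is ±4.2 (passes).

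**4. Simulated probability of passing** (B = 15, that is 5 points per zone; closed zone noise scaled to lung SD 11.7; each subject's side drawn at random)

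| Planned resections | Sides | Primary rule | Right-lung-share interval |
|---|---|---|---|
| 40/40/20 mix | 50:50 | about 99.9% | about 2% |
| 40/40/20 mix | 60:40 | about 99.9% | about 2% |
| Whole lung | 50:50 | about 98% | about 2% |
| 40/40/20 mix, no bias | 50:50 | about 100% | about 100% |

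With sides fixed at exactly 16:16, the whole-lung figure is above 99.9%.

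**5. Dependence on side mix** (whole lung, sides fixed, SD 11.7)

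| Bias | 50:50 | 62.5:37.5 | 69:31 | 75:25 | One side only |
|---|---|---|---|---|---|
| 16 points | 99.9% | 95% | 80% | 52% | 0.5% |
| 20 points | 99.6% | 75% | 37% | 9% | 0% |

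**6. The other planned analyses under B = 15.** Each zone mean sits on the 5-point limit, so a given zone passes about 2.5% of the time. All six zones pass in about 0% of trials. In the 40/40/20 mix, about 24 to 30% of patients lie beyond 14.7 points (lung SD 8.3 to 11.7), against 5 to 15% with no bias.

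**The case against.** Several points on the other side are sound.

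- **The plan is not blind to this bias.** A reader might infer that three zones at 5 points each allow 15 points for a lung. They do not: the whole interval must lie inside the limit in every zone, so a 15-point lung shift almost surely fails. The patient-level analysis and the zone listing would also show it. What remains is that neither affects the primary declaration. A by-zone failure also does not by itself identify a left-right bias: at lung SD 11.7 all six zones pass in only about 22% of trials with no bias at all (about 92 to 93% at SD 8.3).
- **Most patients need not be misjudged beyond the margin.** A reader might infer that equivalence is declared although each patient's error exceeds 14.7 points. At B = 15 the expected error is 5, 10 or 15 points for one, two or three zones. Only whole-lung resections exceed the margin, and in the 40/40/20 mix 80% of subjects are inside it.
- **The inputs are assumed.** The documents give no side split, no mix of extents and no evidence of a bias. In a one-sided sample the primary rule would catch it.
- **The hypotheses openly concern the mean, and the endpoint was revised after discussion with FDA (SAP 9.2).** So the rule is not failing its own stated test. The reason given for that revision is removal of baseline FEV1; it does not address pooling over sides.

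A reader might also want lung share as a second condition for success. That is a debatable trade-off: with a 10-point lung bias, inside the margin, the lung-share test passes only about 59% of the time at SD 11.7 (about 88% at SD 8.3). A rule triggered when right and left means differ in sign would be worse, since it fires in about half of trials with no bias.

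**Conclusion.** The cancellation follows from the SAP's own definitions. With roughly balanced sides, the primary rule can declare equivalence with high probability (about 98% to 99.9% in the settings above) when the mean lung-share bias is at or above 14.7 points. This rests on n = 32, SD 11.7, a bias spread evenly over zones, and assumed side and extent mixes. It weakens steadily with imbalance. The documents support a statement about what the primary rule permits. They do not support saying that such a bias exists, that the whole plan would miss it, or that the primary test is invalid for the mean it targets. This should be fixed before unblinding, but it is not a defect that must stop the analysis.

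**What to change.** In SAP 4.4.1, pre-specify as supportive analyses of the primary endpoint, on the Efficacy Analysis Set:

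1. The within-subject 129Xe minus 133Xe difference in right-lung share (sum of the three right zones; the left lung is its mirror image), with the same t-based 95% interval, read against ±14.7%. The margin carries over because SAP Section 3 derived it for one lung: "Assuming the removed lung contributed 50% of total function".
2. The primary mean difference with its 95% interval separately for right- and left-sided planned resections, with side added to the Section 6 subgroups.

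State that the primary result will be reported together with item 1. If the interval in item 1 is not within the margin, the conclusion is limited to the pooled mean and does not claim agreement on left-right distribution. Do not add a co-primary condition or a rule based on opposite signs. Lung share cannot detect an upper-lower bias, so the by-zone analysis stays as it is.

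The cost is one SAP paragraph, one more table and a possible qualification of the claim. No new data are needed, since the efficacy listing already holds all six zones for both scans and the zones expected to be resected. SAP Section 1 allows documented updates before unblinding.

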**Figure 1**      **6 Lung Zones**

The sample mean ( $\bar{d}$ ) and standard deviation (sd) of the within-subject difference of the predicted remaining proportion of function between the two methods will be estimated and the 95% CI for the mean difference will be computed using the standard formula

$$\bar{d} \pm t(n-1, 0.975) * sd / \sqrt{n},$$

where  $t(n-1, 0.975)$  denotes the 97.5th percentile of the t distribution with  $n-1$  degrees of freedom. If the 95% CI for the mean within-subject difference of the predicted remaining proportion of function from each scan is contained within the interval (-14.7%, +14.7%), equivalence will have been demonstrated. In terms of a hypothesis testing framework, let  $\Delta$  denote the true mean within-subject difference. The null ( $H_0$ ) and alternative ( $H_A$ ) hypotheses are:

$H_0: |\Delta| > 14.7\%$

$H_A: |\Delta| < 14.7\%$

The listing for the efficacy data will present data for all 6 zones for both imaging methods and indicate the zones expected to be resected.

#### 4.4.2. Secondary Efficacy Analyses

##### 4.4.2.1. By-Zone Analysis

The by-zone secondary analysis for this study will be evaluated by comparing the individual percentage function assessments (fraction of ventilation) from each of the 6 zones as derived from the  $^{129}\text{Xe}$  and the  $^{133}\text{Xe}$  ventilation images. The equivalence analysis will be conducted using similar methodology to that in the primary efficacy analysis, and the equivalence margin will be  $\pm 5$  percentage points. Thus, for each of the 6 zones, equivalence will have been demonstrated if the 95% CI for mean difference between the 2 methods is contained within the interval (-5%, +5%).

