### 8.7. Secondary Efficacy Analysis

The post-operative secondary analysis for this study will be to test the mean difference in predicted post-operative FEV1 (measured in L/sec) values as measured using hyperpolarized  $^{129}\text{Xe}$  gas MRI and  $^{133}\text{Xe}$  scintigraphy (reference standard) relative to the final post-operative FEV1 value (spirometry). The secondary equivalence analysis will be conducted using the same methodology and same equivalence margin as specified for the primary analysis.

The 6-zone secondary analysis for this study will be to evaluate the individual percentage function assessments from each of the 6 zone analyses from both the  $^{129}\text{Xe}$  and the  $^{133}\text{Xe}$  ventilation images. The equivalence margin will be 5 percentage points. Thus, for each of the six zones, equivalence will have been demonstrated if the 95% CI for the mean difference is contained within the interval (-5%, +5%).

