## 2. DETERMINATION OF SAMPLE SIZE

The sample size required to demonstrate equivalence is driven by 2 factors: 1) the intra-subject variability of the difference between the predicted post-operative FEV1 from the 2 methods, and 2) the pre-specified equivalence margin. From prior literature, the intra-subject variability for  $^{133}\text{Xe}$  scintigraphy leads to an estimated variability in predicted post-operative FEV1 of 0.21 L. Similarly, prior studies have suggested that the equivalence margin between the 2 imaging techniques currently used for resection planning is 0.3 L. Using these assumptions, and based on

the use of a two-sided test at the  $\alpha = 0.05$  level of significance, a sample size of 15 subjects is required for 90% power. However, given limited literature on  $^{133}\text{Xe}$  variability, we have accounted for the possibility that it could be higher. If true variability is 0.32 L, then a sample size of 32 subjects will provide 90% power to establish equivalence.

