### 4. STATISTICAL METHODS

All final statistical analyses will be performed by the sponsor or designee after the study is completed and the database is locked and released.

All descriptive statistics for continuous variables will be reported using the number of observations (n), mean (arithmetic unless otherwise specified), standard deviation (SD), median, minimum and maximum. Categorical variables will be summarized as the number and percentage of subjects.

All inferential statistics will be based on the 5% level of significance (two-sided).

All data from this study will be presented in listings. All listings will be sorted by treatment sequence, subject number, and visit date, as applicable.

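### The by-zone analysis allows six separate equivalence claims from unadjusted 95% CIs, so the chance of a false zone claim is not held at 2.5%: about 5% with two zones at the margin, up to about 14% in the extreme case

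*SAP*

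**What the plan says.** SAP 4.4.2.1 compares the two scans zone by zone with a margin of ±5 percentage points and states: "for each of the 6 zones, equivalence will have been demonstrated if the 95% CI for mean difference between the 2 methods" lies inside that margin. It takes its method from the primary test: "The equivalence analysis will be conducted using similar methodology to that in the primary efficacy analysis". Protocol 8.7 has the same rule: "for each of the six zones, equivalence will have been demonstrated if the 95% CI for the mean difference is contained" within the same limits. SAP 4 sets one level for everything: "All inferential statistics will be based on the 5% level of significance (two-sided").

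Neither document gives a multiplicity adjustment, a testing order, a condition on the primary result, or a rule that all zones must pass. SAP 9, which lists changes from the protocol, adds nothing on this.

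The verdict wording matches that of the primary test in SAP 4.4.1. The SAP has a separate exploratory section (4.5), and the by-zone analysis is not in it. SAP 4.4.2.2 now compares post-operative FEV1 by tests of zero difference, so the by-zone analysis is the only secondary analysis that still has an equivalence rule.

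**The concern.** Each zone has its own pass rule, and each pass counts as equivalence demonstrated. That gives six chances of a false claim, while the 2.5% limit applies to each zone alone. The documents also do not say what a mixed result would mean. If some zones pass and others fail, the passing zones could be reported as demonstrated in a study that SAP 1 calls pivotal, with no stated control over the error rate of that set of claims. At stake is the reading of the regional secondary objective, not the primary conclusion.

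**Working it through.** **Inputs.** From the documents: six zones; margin ±5 points; 95% CI per zone (SAP 4.4.2.1); paired t interval (SAP 4.4.1); 32 subjects (SAP 2). On dependence, SAP 4.4.1 says "The sum of the resected zone(s) plus the non-resected zones equals 100" per cent, so the six zone differences sum to zero in each subject. The documents give no SD for a zone difference, so 3 to 15 points is an assumed range.

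**The plan's own figures.** The documents state no error rate for the set of zones. The figures that can be reproduced are the sample sizes, and they confirm the test level. A 95% CI inside a margin is two one-sided tests at 2.5% each. Reading the stated variability as a per-method SD, the SD of the difference is √2 × SD. The normal approximation at zero true difference is n = [√2 × SD × (1.960 + 1.645) / 0.3]².

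- SD 0.21 L: 12.7; with the exact t calculation, 15 (power 0.906).
- SD 0.32 L: 29.6; with the exact t calculation, 32 (power 0.905).

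Both match SAP 2. A 90% CI would give 13 and 27. The reference level for one equivalence test in this plan is therefore one-sided 2.5%.

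**Simple bounds for k zones truly at the margin.** If the tests were independent, the chance of at least one false claim would be 1 − 0.975^k:

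- k = 2: 4.9%
- k = 4: 9.6%
- k = 6: 14.1%

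Under any dependence the six-zone limit is 6 × 2.5% = 15%.

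**With the sum-to-zero constraint.** Independence cannot hold exactly. With equal correlations ρ, the variance of the sum is proportional to 6 + 30ρ = 0, so ρ = −0.2. Simulated with n = 32:

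| True zone differences (points) | Assumed SD | At least one false zone claim |
|---|---|---|
| one at +5, five at −1 | 3–8 | 2.3–2.6% |
| one at +5, one at −5, four at 0 | 3–8 | about 5% |
| two at +5, two at −5, two at 0 | 3–8 | about 9% |
| three at +5, three at −5 | 3–8 | 13.4–14.0% |
| three at +5, three at −5 | 12 | about 11.5% |
| three at +5, three at −5 | 15 | about 3.5–4% |

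An assumed positive correlation within each lung lowers the six-zone figure to about 11–13% (SDs 3–8.3).

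The fall at large SDs arises because the interval becomes too wide to fit. With t(31, 0.975) = 2.04, the typical half-width at SD 15 is 2.04 × 15/√32 = 5.4 points, which is more than the margin of 5. At SD 8 it is 2.04 × 8/√32 = 2.9.

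**With Holm at a one-sided family level of 2.5%,** the rate was about 2.5% or lower in these settings, within simulation error.

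**The case against.** The strongest reply is that a family-wise rate matters only if one passing zone counts as success, and neither document says so. The zone objective is to evaluate regional defects, whereas the FEV1 objective next to it speaks of demonstrating equivalence. The SAP 4.4.1 listing shows all six zones for both methods. Six fully reported statements, each with its own 2.5% error, can be defended for a secondary evaluation. This stands if the results are descriptive. It does not fit the present text, which uses the primary test's verdict wording for each zone.

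A reader might also infer four stronger things that the documents do not support:

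- **That 14% is the error rate to expect.** It needs all six true differences at the margin. The average share is 100/6 = 16.7%, so that is a relative bias of about 5/16.7 = 30% in every zone at once.
- **That sum-to-zero pushes several zones to the margin together.** It does not: +5 in one zone can be offset by −1 in each of the others, and the rate is then about 2.5%.
- **That the inflation comes from not testing the primary endpoint first.** It comes from six unadjusted tests. Zone shifts of 5 points are compatible with a primary difference inside ±14.7: one resected zone gives 5, and two shifted the same way give 10.
- **That the primary conclusion is weakened.** There is one primary endpoint and one primary test, and the zone rule plays no part in it.

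**Conclusion.** The concern holds as a limited one about a secondary analysis. The text permits six claims of demonstrated zone equivalence, and the chance that at least one is false is not held at the single-zone 2.5%. It is about 5% with two zones truly at the margin, about 9% with four, and up to about 14% in the extreme case of six. These figures assume 32 subjects, normal differences and zone-difference SDs of 3 to 8 points. If the true SD is much larger, the inflation shrinks and at SD 15 has largely gone. If only one zone is at the margin, there is none. Whether strict control is needed depends on whether the sponsor intends to claim equivalence for single zones, and the documents leave that open.

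**What to change.** In SAP 4.4.2.1, state which kind of result the zone analysis is, and document the change before unblinding as SAP 1 requires.

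1. **If single-zone equivalence is to be claimed,** apply Holm across the six tests at a one-sided family level of 2.5%. Take each zone's p-value as the larger of its two one-sided p-values. Compare the smallest with 0.025/6 = 0.0042, the next with 0.025/5 = 0.005, and so on to 0.025, stopping at the first failure.
2. **Otherwise,** present the six 95% CIs as descriptive and remove the statement that equivalence is demonstrated.
3. **An acceptable alternative** is one joint claim, made only if all six 95% CIs lie within ±5 points. This needs no alpha adjustment.

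A condition that the primary test passes first may be added as a separate ordering rule. It does not replace any of these.

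**Cost.** The change is wording only, with no new data. For Holm at zero true difference, average zone power goes from about 99% to 98.8% at SD 6, and from about 86% to 70% at SD 8. The joint claim has power of about 99.7%, 95%, 43% and under 0.1% at SDs of 5, 6, 8 and 12, so it could become unwinnable if zone variability is high. The descriptive option costs no power but gives up the claim.
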